12.4.2 Secondary Safety Endpoints

• Incidence of AEs and Serious (Non-Primary) AEs during 12 Month Follow-up

Incidence of Serious Non-Primary AEs and All AEs during the 12 months follow-up will be reported by coded AE categories in three timeframes (ablation to \leq 7 days, \geq 7 to 30 days post ablation and \geq 30 days). AEs will be evaluated by causality and treatment groups using descriptive statistics.

The primary safety outcomes will be presented in the SP, AT populations and for Calibration Roll-in subjects. Listing of will be provided for subjects in the SP.

• PV Stenosis at 3 Months Post Ablation

Incidence of PV narrowing 3 months post ablation (<50%, 50-70%, ≥70% diameter reduction in diameter of pulmonary vein from baseline CT/MRA scan) will be reported overall and by

ablation targets. The percent of subjects with PV narrowing for subjects undergoing an RF ablation procedure using nMARQ system will be presented descriptively.

The outcomes of 3-month PV narrowing will be presented in the ITT subjects in the nMARQ group and for Calibration Roll-in subjects.

• Incidence of AEs and Serious (Non-Primary) AEs during 2nd and 3rd Year Follow-up

All AEs, including Serious Non-Primary AEs and Non-serious AEs, during the 2nd (366-730 days post the index procedure) and 3rd year (>730 days post the index procedure) follow-up period will be summarized by coded AE categories, causality, timeframes and treatment groups using descriptive statistics.

The outcomes of 2nd- and 3rd-year (S)AEs will be presented in the SP, AT populations and for Calibration Roll-in subjects. Listing will be provided for subjects in the SP.

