10.1.3 Primary Adverse Event

A **Primary AEs** is an event listed in Table 10.1.3A which occurs within the first week (7 days) following an ablation procedure. Primary AEs are considered SAEs.

Table 10.1.3A: Primary Adverse Events

Primary Adverse Event	Description/Criteria
Death	Adverse event resulting in patient death.
Atrio-esophageal Fistula*	Connection between the atrium and the lumen of the esophagus as evidenced by documentation of esophageal erosion combined with evidence of a fistulous connection to the atrium.
Cardiac Tamponade/Perforation	The development of a significant pericardial effusion during or within 30 days of undergoing the index AF ablation procedure. A significant pericardial effusion is one which results in hemodynamic compromise [†] , requires elective or urgent pericardiocentesis, or results in a 1 cm or more pericardial effusion as documented by echocardiography. 
 Cardiac tamponade/perforation should also be classified as: 
 Early – diagnosed prior to discharge Late – following initial discharge from the hospital (see Safety requirement below)
Myocardial Infarction	Presence of any one of the following criteria: 
 Detection of ECG changes indicative of new ischemia (new ST-T changes or new LBBB) which persist for more than 1 hour Development of new pathological Q waves on ECG Imaging evidence of new loss of viable myocardium or new regional wall motion abnormality
Stroke	Stroke/CVA is an acute symptomatic episode of neurological dysfunction attributed to a vascular cause (ischemia or hemorrhage) in which symptoms last more than 24 hours, or if symptoms last less than 24 hours, a brain imaging study demonstrates infarction.
Cerebrovascular Accident (CVA)	
Thromboembolism	Formation in a blood vessel of a clot (thrombus) that results from the breaking loose of all or part of an existing thrombus, which is then carried by the blood to lodge in/occlude a more distal vascular site.
Transient Ischemic Attack	Acute episode of temporary (<24 hrs) and focal loss of cerebral function of vascular (occlusive) origin as determined by the consulting neurologist.
Diaphragmatic Paralysis	Change in baseline diaphragmatic functioning as evidenced by elevation of the diaphragm above the normal range but not due to a pulmonary process such as atelectasis.

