11.8.1 Incidence of AEs and SAEs during 12 Month Follow-up

Serious AEs will be reported by three timeframes (ablation to ≤ 7 days, >7 to 30 days post ablation and >30 days). AEs and serious AEs will be evaluated by causality and severity and treatment groups using descriptive statistics.

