7.2 Secondary Endpoints

Acute Effectiveness:

• Acute effectiveness is defined as complete PVI confirmation as documented by confirmed entrance block (i.e., complete PVI with or without the use of the toolkit's focal catheter).

One-Year Effectiveness:

• Freedom from AF/AFL/AT off antiarrhythmic drug therapy as assessed from the end of the 3-month blanking period to 12 months following the ablation procedure.

Long-Term Effectiveness:

- Freedom from AF/AFL/AT off antiarrhythmic drug therapy as assessed from the end of the 3-month blanking period to 2 year following the ablation procedure.
- Freedom from AF/AFL/AT off antiarrhythmic drug therapy as assessed from the end of the 3-month blanking period to 3 year following the ablation procedure.

Long Term Safety:

- Incidence of AEs and serious adverse events (SAEs) during the 12 month follow-up period post ablation procedure.
- Assessment of PV stenosis at 3 months post-ablation.
- Incidence of AEs and serious adverse events (SAEs) during the 2nd and 3rd year follow-up period post ablation procedure.

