12.4.1 Primary Safety Endpoints

The incidence of early-onset Primary Adverse Events is the percentage of patients with at least one primary adverse event with onset on Day 0 through Day 7 except for pulmonary vein (PV) stenosis and atrio-esophageal fistula that could occur greater than one week (7 days) post-procedure. The number of primary adverse events (PAE) and the number of subjects experiencing primary adverse events will be reported.

The primary safety outcomes will be presented in the SP, AT populations and for Calibration Roll-in subjects. Listing of PAEs will be provided for subjects in SP.

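### SAP 12.4.2 splits serious adverse events into primary and non-primary and plans no combined SAE incidence, although SAP 7.2 names SAE incidence as the endpoint

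*SAP*

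**What the plan says.** SAP 7.2 lists among its long-term safety endpoints "Incidence of AEs and serious adverse events (SAEs) during the 12 month follow-up period post ablation procedure", with a parallel endpoint for years 2 and 3. Neither is limited to non-primary events.

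Protocol 10.1.3 states that "Primary AEs are considered SAEs". A Primary AE is an event in Table 10.1.3A "which occurs within the first week (7 days) following an ablation procedure"; pulmonary vein stenosis and atrio-esophageal fistula stay primary after that window.

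The SAP analyses serious events in two places:

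- SAP 12.4.1 covers primary events: "The number of primary adverse events (PAE) and the number of subjects experiencing primary adverse events will be reported", in the SP, the AT population and the roll-in subjects. It adds: "Listing of PAEs will be provided for subjects in SP".
- SAP 12.4.2 covers the rest. For 12 months, "Incidence of Serious Non-Primary AEs and All AEs during the 12 months follow-up will be reported by coded AE categories", in three timeframes. For the later years the scope is "All AEs, including Serious Non-Primary AEs and Non-serious AEs, during the 2nd" and 3rd year.

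The protocol's own analysis text (11.8.1) reports serious AEs in three timeframes without excluding the primary ones, and adds that "AEs and serious AEs will be evaluated by causality and severity and treatment groups using descriptive statistics". Protocol 11.8.3 also asks for severity in years 2 and 3. SAP 12.4.2 names causality and treatment group for 12 months, and category, causality, timeframe and treatment group for the later years. Severity appears in neither.

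**The concern.** An endpoint section and its analysis section should describe the same quantity. Here SAP 7.2 promises SAE incidence, and SAP 12.4 provides primary events, serious non-primary events and all AEs, but not all SAEs.

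This matters more than usual because the closeout report carries no efficacy data and no inferential statistics (SAP 12.0). Descriptive safety is its main clinical content. A reader who wants the proportion of subjects in each arm with a serious event, above all in the first week when most Primary AEs are by definition counted, would have to assemble it from separate tables, and subject counts cannot be assembled that way.

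**Working it through.** The plan states no figure that this point disputes, so there is nothing to reproduce. The check sets the texts side by side, then shows with simple bounds what the planned summaries leave undetermined.

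**Step 1. Is any planned category equal to all SAEs?**

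| Planned summary | Primary SAEs | Non-primary SAEs | Non-serious AEs |
|---|---|---|---|
| SAP 12.4.1, Primary AEs | yes | no | no |
| SAP 12.4.2, serious non-primary | no | yes | no |
| SAP 12.4.2, all AEs | yes | yes | yes |
| Endpoint in SAP 7.2, SAEs | yes | yes | no |

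No planned row matches the last one.

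**Step 2. Can it be derived from the planned rows?** Event counts can be added, because an event is either primary or not. Subject counts cannot. Let p be the proportion of subjects with a Primary AE and q the proportion with a serious non-primary AE. Then

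P(any SAE) = p + q − P(both).

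P(both) is not reported. It can be as low as 0 (when p + q is at most 1) and as high as the smaller of p and q, so

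max(p, q) ≤ P(any SAE) ≤ p + q.

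If the two kinds of event were independent, P(any SAE) = 1 − (1 − p)(1 − q).

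**Step 3. Illustration.** Inputs: p = 8.6%, the planning rate in SAP 10.0 and protocol 11.3.1. The documents give no non-primary SAE rate, so q is an assumption and is varied.

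| q (assumed) | Lower bound | If independent | Upper bound |
|---|---|---|---|
| 2% | 8.6% | 10.4% | 10.6% |
| 5% | 8.6% | 13.2% | 13.6% |
| 10% | 10.0% | 17.7% | 18.6% |
| 20% | 20.0% | 26.9% | 28.6% |

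At q = 10%: lower bound max(8.6, 10) = 10.0%; upper bound 8.6 + 10 = 18.6%; independence 1 − 0.914 × 0.900 = 0.1774. The range is 8.6 percentage points wide.

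**Step 4. Severity.** Protocol 10.3 requires severity for each AE, and protocol 10.6 has the safety committee adjudicate it for SAEs. The data are therefore collected; the SAP does not use them in these summaries.

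**The case against.** The strongest reply is that nothing is concealed. Primary AEs have their own analysis with event counts, subject counts and a listing, and as AEs they also enter the all-AE category. The SAP labels its serious category openly as non-primary and never presents it as the total. Subject-level data would let anyone compute the total. The SAP is a descriptive closeout plan with no hypothesis tests, and SAP 2.0 says its methods follow the Closeout Plan and override those of the protocol. All of this stands, and it limits the point to a missing summary. It does not remove the mismatch between SAP 7.2 and SAP 12.4.2, because both belong to the overriding document.

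Several stronger readings are tempting but unsupported:

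- *The report leaves out the gravest events.* It does not. Primary events are in SAP 12.4.1, and a death or stroke more than 7 days after ablation counts as serious non-primary.
- *Late stenosis or fistula has no place in years 2 and 3.* The governing term there is all AEs; the two named classes are given as included, not as the whole. SAP 12.4.1 also covers these two events after day 7.
- *Most SAE subjects would be missing.* The REVOLUTION summary (protocol 3.3.3) gives 9 subjects with a Primary AE and 2 with SAEs possibly related to the procedure, and 9/(9 + 2) = 82%. That denominator holds only Primary AEs and related SAEs. The SAP table counts SAEs whatever their cause, and no count of unrelated SAEs is given.
- *About 21 of every 250 SAE subjects would be missing.* The product 0.086 × 250 = 21.5 counts subjects with a Primary AE per 250 treated, not per 250 with an SAE, and some of them may also have a non-primary SAE.
- *The severity omission contradicts the SAP.* It departs from protocol text that the SAP overrides; it is unexplained rather than contradictory.

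**Conclusion.** The point holds as a gap between endpoint and analysis. As written, SAP 12.4 does not produce the subject-level SAE incidence, by arm and timeframe, that SAP 7.2 names, and the planned subject counts do not determine it. Its size cannot be fixed from the documents. The 10.0% to 18.6% range rests on the 8.6% planning rate and an assumed 10% non-primary rate, and shows only how far two marginal rates can leave the total open.

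No event goes unreported, and no test or trial conclusion depends on this. It should be corrected because the stated endpoint is otherwise not delivered and the correction is nearly free. The loss of severity is secondary.

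The conclusion rests on the SAP text alone. The Closeout Plan and the Appendix A shells were not available, and an any-SAE row or a severity column there cannot be excluded.

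**What to change.** In SAP 12.4.2, and in the matching table shells:

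1. Add a row *Any SAE (primary or non-primary)*, giving the number and percentage of subjects, each counted once, and the number of events. Show it by timeframe and treatment group in the 12-month table and in the year-2 and year-3 tables.
2. Keep *Serious Non-Primary* as a sub-row beneath it.
3. Restore the breakdown by severity from protocol 11.8.1 and 11.8.3, or state why the closeout report omits it.
4. If the Closeout Plan or Appendix A already contains these rows, align the wording of 12.4.2 with them.

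The cost is a short text change and a few table rows from data already collected. The total SAE figure will be higher than the non-primary row alone wherever a subject had only a primary event.

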11.4 Analysis Populations

The study contains two treatment arms with subjects receiving either nMARQ or TC ablation. The following analysis populations will be used to complete the analyses prespecified in this study:

Intent-to-treat population (ITT): The ITT subject population will include all randomized patients who have the ablation catheter inserted. They will be analyzed as randomized. Lost-to-follow-up and withdrawn / early termination subjects post randomization are included in the ITT population. Calibration Roll-in cases will not be included.

As-treated population (AT): The AT subject population will include all randomized patients who have the ablation catheter inserted. They will be categorized by the treatment received if this deviates from the treatment randomized. Calibration Roll-in cases will not be included.

Per Protocol Population (PP): The PP subject population will include randomized subjects who satisfy the following criteria. Calibration Roll-in subjects will not be included.

- have undergone RF ablation,
- are treated with the study catheters as randomized (nMARQ or TC),
- are in compliance (no major protocol deviations) with the study protocol, and
- have been treated for the study-related arrhythmia.

SNA Population (SNAP): The SNAP will include all subjects who are enrolled and randomized within the Main Study and who further satisfy specific inclusion and exclusion criteria and provide additional consent to participate in the SNA. Eligible SNA subjects will have undergone RF delivery with the study ablation catheters and will have successfully completed pre- and post-ablation brain MRI examinations, NIHSS Questionnaires, and general neurological

assessments.

Safety Population (SP): The SP will include all subjects who have undergone insertion of an ablation catheter. The subjects will be analyzed according to the treatment they actually received regardless of the Group they are randomized to. The calibration roll-in cases will be included in the SP.

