11.8 Secondary Safety Endpoints Analyses

The secondary safety analysis will be conducted based on the SP population. The Roll-in subjects will only be included in the secondary safety analyses and will be analyzed separately from subjects included in the Main Study.

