11.8.2 PV Stenosis at 3 Months Post Ablation

Incidence of PV stenosis ($<50\%$, $50-70\%$, $\geq 70\%$ diameter reduction in diameter of pulmonary vein from baseline CT/MRA scan) will be reported as the rate of incidence for Test subjects undergoing an RF ablation procedure. This rate of incidence as well as the 95% confidence intervals will be presented descriptively for test group.

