9.1 Intent-to-Treat Population (ITT)

The ITT subject population will include all randomized patients who have the ablation catheter inserted. They will be analyzed as randomized. Lost-to-follow-up and withdrawn / early termination subjects post randomization are included in the ITT population. Calibration Roll-in cases will not be included.

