9.2 As-Treated Population (AT)

The AT subject population will include all randomized patients who have the ablation catheter inserted. They will be categorized by the treatment received if this deviates from the treatment randomized. Calibration Roll-in cases will not be included.

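### SAP 12.4.2 presents 3-month PV narrowing in the as-randomised nMARQ group, although the same paragraph and the other safety outcomes go by treatment received; the population should be stated by treatment received

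*SAP*

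**What the plan says.** The PV paragraph of SAP 12.4.2 describes its population twice. First: "The percent of subjects with PV narrowing for subjects undergoing an RF ablation procedure using nMARQ system will be presented descriptively". Then: "The outcomes of 3-month PV narrowing will be presented in the ITT subjects in the nMARQ group and for Calibration Roll-in subjects".

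The SAP's definitions separate the two. For ITT (SAP 9.1), catheter insertion after randomisation is enough, and "They will be analyzed as randomized". The AT population (SAP 9.2) is drawn from the same subjects, but "They will be categorized by the treatment received if this deviates from the treatment randomized".

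Primary adverse events (SAP 12.4.1) and the 12-month and second- and third-year adverse events (SAP 12.4.2) are presented in the SP and AT populations and for roll-ins. PV narrowing is the only safety outcome in those two sections assigned to ITT, and no reason is given.

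In the protocol, section 11.8 states: "The secondary safety analysis will be conducted based on the SP population". Section 11.4 says of that population: "The subjects will be analyzed according to the treatment they actually received regardless of the Group they are randomized to". Section 11.8.2 is less explicit; PV stenosis "will be reported as the rate of incidence for Test subjects undergoing an RF ablation procedure".

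**The concern.** PV narrowing after ablation is a harm of the device used, so the natural population is subjects whose veins were treated with that device. The table covers nMARQ only: CT/MRA is scheduled for that group alone (Protocol Table 9.9A and section 9.10). With no Control column, as-randomised grouping has no comparison to protect.

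The top narrowing category, 70% or more, is also a primary adverse event (Protocol Table 10.1.3A), including when it occurs after day 7 (SAP 7.1). SAP 12.4.1 reports it by treatment received. A severe stenosis in a subject treated off-assignment could therefore be an nMARQ event in one table and be missing from the other. The reverse can also happen: a subject randomised to nMARQ but ablated with TC can enter the nMARQ denominator.

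The plan allows for such subjects. The AT and SP definitions both provide for treatment that differs from assignment, and the PP definition makes treatment as randomised a separate condition.

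**Working it through.** The plan states no figure on this point, so there is none to reproduce. The check has two parts: comparing the definitions, then sizing the effect under stated assumptions.

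**Definitions**

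- ITT and AT contain the same people: randomised, ablation catheter inserted, roll-ins excluded. They differ only in the arm label of subjects treated off-assignment.
- With no such subjects, ITT-nMARQ and AT-nMARQ are identical.
- A subject randomised to nMARQ but ablated with TC is in ITT-nMARQ and not in AT-nMARQ.
- A subject randomised to TC but ablated with nMARQ is in AT-nMARQ and not in ITT-nMARQ.

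**Inputs for size**

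- Group size: the ITT population reached 250 (SAP 12.5), so about 125 per arm at 1:1. I take 150 as an assumed upper figure.
- Share treated off-assignment: not given; 2-5% assumed.
- PV stenosis rate: Protocol 4.1 cites 0.32% (acute), 1.3% (persistent) and 3.4% (an older series). These are general ablation figures. No PV stenosis was reported in either earlier nMARQ study (Protocol 3.3.2 and 3.3.3).

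**Expected severe cases at 1.3%**

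- 125 × 0.013 = 1.6; 150 × 0.013 = 2.0.
- One case is worth 1/125 = 0.80 or 1/150 = 0.67 percentage points.

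**Expected misplaced severe cases**

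- Subjects in the wrong set: 0.02 × 125 = 2.5 to 0.05 × 150 = 7.5.
- Misplaced cases: 2.5 × 0.013 = 0.03 to 7.5 × 0.013 = 0.10.

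**Chance that at least one severe case is missing from the ITT table**

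This is 1 − (1 − p)^c, where c is the number randomised to TC but treated with nMARQ and p is the stenosis rate. It assumes all c subjects have paired scans, so it is an upper figure.

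| c | p = 0.32% | p = 1.3% | p = 3.4% |
|---|---|---|---|
| 0 | 0 | 0 | 0 |
| 1 | 0.3% | 1.3% | 3.4% |
| 3 | 1.0% | 3.8% | 9.9% |
| 6 | 1.9% | 7.6% | 18.7% |

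**Dilution in the other direction**

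Suppose there are 2 severe cases among nMARQ-ablated subjects, and 6 of the 125 randomised to nMARQ were ablated with TC. The ITT rate is 2/125 = 1.60%; the rate among those treated with nMARQ is 2/119 = 1.68%.

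**The case against.** The strongest reply is that little is left once the whole text is read together.

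- **The two SAP sentences can be combined.** Read as ITT nMARQ subjects who had RF with nMARQ, they exclude TC-ablated and no-RF subjects. SAP 12.4 also drops subjects with missing outcomes. Discontinued subjects are normally followed for only 30 days (SAP 12.2), so they would not usually have a 3-month scan. This stands and removes most of the dilution. It does not bring in TC-randomised subjects ablated with nMARQ.
- **Those subjects often could not enter the table anyway.** Scans are scheduled for the nMARQ group only, and the baseline scan precedes ablation. This largely stands, though Protocol Table 9.4A lists the baseline CT/MRA without that limit.
- **The SAP supersedes the protocol (SAP 2.0).** True, so the difference from Protocol 11.8 is not an error in itself, and Protocol 11.8.2 speaks of Test subjects. But the inconsistency also lies within the SAP, where that rule does not help.
- **SAP 4.0 words the nMARQ group by device used.** It also presents it as a group into which subjects are randomised. The label has two meanings, which is a reason to clarify it.

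A reader might go further and infer that the table follows the wrong group and cannot agree with the primary adverse event table. The documents do not support that: it requires subjects treated off-assignment, and none are reported. Nor would a common population make the tables match. Primary adverse events are counted over all SP or AT subjects, while narrowing needs paired scans.

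**Conclusion.** The point holds as an inconsistency in wording with a possible, small effect. SAP 12.4.2 names an as-randomised population for a single-arm device-safety outcome, while its own preceding sentence and the neighbouring safety outcomes go by treatment received.

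The consequence depends on subjects treated off-assignment, whose number is not given. With none, the randomised nMARQ groups are the same under either label. At an assumed 2-5%, with 125 to 150 subjects and a 1.3% rate, 0.03 to 0.10 severe cases would be expected to be misplaced. At the zero rate seen in the earlier nMARQ studies, none would be.

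It is tempting to note that one misplaced case would be a large fraction of a 1.3% rate. That describes an unlikely event once it has happened, not the expected distortion.

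Reporting is descriptive (SAP 8.0 and 12.0), so no alpha, power or success decision is touched. A severe stenosis recorded as a primary adverse event would still appear in the as-treated tables and the SP listing. Low priority, but worth correcting.

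**What to change.** Replace the last sentence of the PV paragraph in SAP 12.4.2 with: *PV narrowing will be presented for AT subjects (by treatment received) who had RF delivered with the nMARQ system and have readable baseline and 3-month CT/MRA scans, and separately for Calibration Roll-in subjects.*

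Add a footnote to the table identifying any TC-randomised, nMARQ-treated subject without paired scans, so that the omission is visible.

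The cost is one sentence, one footnote and a changed population filter. No new data are needed, and the denominator may move by a few subjects. The change gives the correct exposure group and removes the ambiguity; it should not be presented as making the PV and primary adverse event tables agree exactly, because their denominators still differ.
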